3.6.2. Columbia Suicide Severity Rating Scale Children's version

Definition:

The C-SSRS-C data will be mapped to Columbia Classification Algorithm for Suicide Assessment (C-CASA) (Guidance for Industry, Suicidality, FDA CDER, September 2010) following C-SSRS Scoring and Data Analysis Guide (February 2013) ([C-SSRS Guide](#)). The following endpoints will be thus considered:

11 preferred C-SSRS categories:

- For Suicidal ideation:
 - Wish to be dead (category 1).
 - Non-specific active suicidal thoughts (category 2).
 - Active suicidal ideation with any methods (not plan) without intent to act (category 3).

- Active suicidal ideation with some intent to act, without specific plan (category 4).
- Active suicidal ideation with specific plan and intent (category 5).
- For Suicidal behaviour:
 - Preparatory acts of behaviour (category 6).
 - Aborted attempt (category 7).
 - Interrupted attempt (category 8).
 - Actual attempt (non-fatal) (category 9).
 - Completed suicide (category 10).
- Self-injurious behaviour without suicidal intent (category 11).

Endpoints derived from these C-SSRS categories:

- Suicidal ideation or behaviour: at least one “yes” answer present at any assessable visit (*i.e. categories 1 to 10 analysable*) during the considered period to any one of the 1 to 10 categories.
- Suicidal ideation: at least one “yes” answer present at any assessable visit during the considered period to any one of the 1 to 5 categories.
- Suicidal behaviour: at least one “yes” answer present at any assessable visit during the considered period to any one of the 6 to 10 categories.
- Suicidal ideation score: maximum suicidal ideation category (1-5 on the CSSRS) among any assessable visit of the considered period; 0 if no ideation is present.

Baseline:

For suicidal ideation and suicidal behaviour (for items and the four associated derived C-SSRS endpoints), baseline will be defined as the value at W000, lifetime.

Analyses:

The 11 preferred C-SSRS categories as well as the four associated derived C-SSRS endpoints will be described during the double-blind (resp. open-label, combined) treatment period (*i.e. periods #2, #4 and #6*). Moreover, a listing of all patients having at least one post-baseline category equal to “yes” will be performed.

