5.6. Participant withdrawal

5.6.1. Withdrawal criteria

Premature discontinuation of IMP during the double blind treatment period (W000-W026) does not mean that the participant prematurely stops the participation in the study.

In the case of premature discontinuation of IMP during the double blind period and, if the patient does not require an important modification on his/her current background medical care, he/she will be invited to complete CARS2, SRS-2, CGI evaluations and AE assessment for W012 (if discontinuation occurs prior to W012) and W026 visit as planned in the investigation schedule (Section 4.2.2).

Important modification of current medical care is defined as follows:

- *Newly initiated formal behavioural, cognitive or cognitive-behavioural therapy*
- *Increase/decrease weekly prescribed hours >25% of behavioural, cognitive or cognitive-behavioural therapy*
- *Newly initiated or recently changed pharmacotherapy:*
 - o *Introduction of a psychotropic medication (considered as forbidden in the study, section 6.3)*
 - o *Introduction or dose increase of an antipsychotic*
 - o *Introduction or dose increase of ADHD treatment*

The following criteria will lead to a premature discontinuation of IMP:

- Serum potassium levels < 3mEq/L
- Any suicide attempt, whatever its severity
- High suicidal risk, according to investigator's judgment or with a suicidal ideation of 4 or 5 on C-SSRS-C
- Nephrocalcinosis observed at the renal ultrasound
- Occurrence of seizure(s)
 - o in a patient without any medical history of seizure.
 - o or in a patient with a medical history of seizure if this require any modification of the on-going anti-epileptic treatment.
- Any symptoms or signs of potential renal function failure.
- eGFR $\leq 80\text{mL}/\text{min}/1.73\text{m}^2$ (estimated glomerular filtration rate, Schwartz formula 2009).
- Clinically relevant nephropathy according to investigator's clinical judgment (based on broader sources including risk factors, medical history, clinical examination and biological parameters).
- Clinically relevant hypercalciuria.

In case of abnormal urinary calcium/creatinine ratio that may be the expression of a clinically relevant hypercalciuria, a retest should be performed as soon as possible. Based on these results, the investigator should have a discussion with the local paediatric nephrologist in order to assess whether it corresponds to the presence of a clinically

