3.1.2. General definitions

Unless specified otherwise in Sections 3.2 to 3.6, the following definitions will be considered:

Three analysis periods will be defined:

- Double-blind period.
- Open-label period.
- Combined period.

For each, start date, stop date, first and last IMP intake date, baseline and under treatment period will be specified.

- Analysable value will be defined as any non-missing value.
- Baseline value will be defined as the last analysable value prior to the first IMP intake of the considered analysis period (*i.e.* before or the same* date as the first IMP intake date).

Note:

- In case of patient included and/or randomised but not treated (*i.e.* patients with treatment duration equal to 0): value at baseline (for the double-blind or combined period) is defined as the last analysable value prior or equal to date of inclusion visit.
 - * For parameters measured the day of inclusion for the double-blind or combined period (resp. the day of W26 or W26B for open-label period) but before the first IMP intake of the considered period.
- Post-baseline value will be defined as any value recorded at a given timepoint after baseline.
 - Change from baseline will be defined as the arithmetic difference between a post-baseline value and the baseline value of the considered period.

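### The four derived C-SSRS-C endpoints ignore a recorded 'yes' on an incomplete form and do not define the result for a child who has only incomplete forms

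*SAP*

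**What the plan says.** SAP 3.6.2 maps C-SSRS-C to eleven categories: 1 to 5 for ideation, 6 to 10 for suicidal behaviour, and 11 for self-injury without suicidal intent. It derives four endpoints from them.

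- Ideation or behaviour: at least one 'yes' in categories 1 to 10 at an assessable visit, a term explained here, and only here, as "categories 1 to 10 analysable".
- Ideation: a 'yes' "answer present at any assessable visit during the considered period to any one of the 1 to 5 categories".
- Behaviour: a 'yes' "answer present at any assessable visit during the considered period to any one of the 6 to 10 categories".
- Ideation score: "maximum suicidal ideation category (1-5 on the CSSRS) among any assessable visit of the considered period; 0 if no ideation is present".

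SAP 3.1.2 supplies the meaning of analysable: "Analysable value will be defined as any non-missing value". SAP 3.6.2 does not override it and makes no exception for a 'yes' on an incomplete form.

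The endpoints are described over safety periods #2, #4 and #6 (SAP 3.6). The eleven single categories are described as well, and the SAP plans "a listing of all patients having at least one post-baseline category equal to" 'yes'. Neither of these outputs is restricted to assessable visits.

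**The concern.** Three of the endpoints ask whether at least one 'yes' occurred, and the fourth is a maximum. One observed 'yes' settles the first kind whatever else is blank, and an observed level is a lower bound for the second. Completeness is needed only to conclude 'no'. The SAP applies the completeness test to both answers, so compared with counting every recorded 'yes' it can drop positive children from the derived counts but never add one.

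At stake is the consistency of the suicidality tables. The same report could show a child with ideation score 0 in one table and a recorded ideation in the listing. Positives are likely to be few in children aged 2 to under 7, so one misclassified child could be a large share of an arm's count.

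**Working it through.** The SAP states no figure to reproduce. The check applies the rule to example records.

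**Inputs**
- Assessable visit: categories 1 to 10 non-missing (SAP 3.6.2 with 3.1.2).
- Scheduled post-baseline forms: W012 and W026 (double-blind), W038 and W052 (open-label), or the withdrawal visit (Protocol 8.2).
- Period #2 ends no later than the last double-blind intake + 2 days (SAP 3.6).
- IMP discontinuation criteria include any suicide attempt and "High suicidal risk, according to investigator's judgment or with a suicidal ideation of 4 or 5 on C-SSRS-C" (Protocol 5.6.1).
- Visits after IMP discontinuation collect CARS2, SRS-2, CGI and adverse events, with no C-SSRS-C (Protocol 4.2.2).

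**Readings compared**
- (a) Literal: all of categories 1 to 10 non-missing.
- (b) Only the endpoint's own categories non-missing.
- (c) Any 'yes' counts; completeness is needed only for 'no'.

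**Records** (hypothetical; items not mentioned are answered 'no')
1. W012: categories 1 and 2 'yes', category 8 missing. W026: complete, all 'no'.
2. W012: categories 1 and 2 'yes', category 3 missing. W026: complete, all 'no'.
3. Only form in the period: categories 1, 2 and 4 'yes', categories 6 to 10 missing.
4. Only form in the period: category 9 'yes', category 3 missing.

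Results are in the order ideation or behaviour / ideation / behaviour / score. U means the SAP does not define the result.

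| Record | (a) literal | (b) own categories | (c) any 'yes' counts | In listing |
|---|---|---|---|---|
| 1 | no / no / no / 0 | no / yes / no / 2 | yes / yes / no / 2 | yes |
| 2 | no / no / no / 0 | no / no / no / 0 | yes / yes / no / 2 | yes |
| 3 | U / U / U / U | U / yes / U / 4 | yes / yes / missing / 4 | yes |
| 4 | U / U / U / U | U / U / yes / U | yes / missing / yes / missing | yes |

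Records 1 and 2 show the wrong classification. Reading (b) repairs the ideation endpoint and score in record 1 but not the combined endpoint, and it does not repair record 2. Records 3 and 4 show the gap: no visit is assessable under (a), and the wording "among any assessable visit of the considered period; 0 if no ideation is present" does not settle whether 0 is the default.

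**Size.** Let q be the share of forms with at least one of categories 1 to 10 missing, unrelated to the answers (assumed; no rate is given). A child positive at a single visit goes uncounted with probability q: 2%, 5% or 10% for q = 0.02, 0.05 or 0.10. With about 100 children per arm, one uncounted child is 1/100 = 1 percentage point.

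**The case against.** **Tempting stronger readings.** A reader might infer that a level-4 ideation at W012 followed by a clean W026 would be scored 0. The documents do not support that sequence. Level 4 or 5 leads to IMP discontinuation, the later W026 visit has no C-SSRS-C, and period #2 would already have closed. A 0 would need a complete all-'no' form within 2 days of the last intake, while Protocol 5.6.2 allows up to a week for the withdrawal visit. A reader might also infer that an attempt recorded on a partial form becomes 'no'. If that is the only form, the result is undefined, as in record 4.

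**Downward bias is not general.** SAP 3.1.1 shows no 'Missing' class unless the table templates say so. A child with no assessable visit may therefore leave numerator and denominator together. Take 100 children with one form each, 2% positive, and 10% of forms incomplete independently of status, the missing item never being the 'yes' (all assumed). The current rule gives 1.8/90 = 2.0%; counting every 'yes' gives 2.0/90.2 = 2.2%. Counts fall under the current rule, but percentages need not. They are pulled down when the child also has a complete all-'no' form and so stays in the denominator.

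**No 'yes' disappears from the report.** The category table and listing keep it, and clinically relevant events are also collected as adverse events. Trained investigators complete the form, and the data are monitored and queried, so q may be small. The SAP also cites a scoring guide and separate table templates, neither of which is available here; they may handle partial forms.

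All of this limits the size. It does not alter what the SAP text says for records 1 and 2, or fill the gap in records 3 and 4.

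**Conclusion.** The point holds in a limited form. On the plain reading of SAP 3.6.2, a child still on treatment with a lower-level 'yes' on a partial form and a complete all-'no' form in the same period is classified 'no' with score 0, contradicting two of the SAP's own outputs. For a child whose only form in the period is partial, the result is undefined. That situation is more likely after ideation of 4 or 5 or an attempt, because these lead to IMP discontinuation.

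The conclusion assumes that "categories 1 to 10 analysable" means all ten categories and that the repeated term carries this to the other three endpoints. If a programmer used only each endpoint's own categories, record 2 and the combined endpoint would still fail.

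The primary analysis is untouched, and SAP 3.4.1 provides no p-value for any other analysis. The number of children affected cannot be computed from the documents. This is a minor correction that is worth making.

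**What to change.** Replace the assessable-visit condition in SAP 3.6.2 with:

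> Any recorded yes counts for the endpoint, whatever other categories are missing. A child is classified as no (ideation score 0) only if at least one visit in the period has all categories of that endpoint (1-5, 6-10 or 1-10) analysable and no yes is recorded in the period. Otherwise the endpoint is missing. The ideation score is the highest category answered yes. The number of children with a missing endpoint is reported by arm.

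The cost is this wording and a small programming change. There is one statistical downside: partial forms with a 'yes' are kept while partial forms without one stay unclassified, so percentages among classified children may be slightly higher (2.2% against 2.0% in the illustration above). Showing counts over the Safety Set alongside makes this visible; in the same illustration that is 2.0/100 = 2.0%. Where an ideation item is missing, the score is a lower bound, and a table footnote should say so.

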3.6.3. Clinical laboratory evaluation

Definition:

- A laboratory value is considered as analysable if non-missing and not flagged in the ClinTrial database as "not analysable".
- The analyses will be performed on periods #2, #4 and #6.
- A value is considered as occurring during the considered period if the sampling date is between the start and last date of the considered period.
- Baseline for each period is defined in Section 3.1.2.
- For each considered period:
 - High emergent abnormal value under treatment according to the laboratory reference ranges is defined as value \leq ULN (Upper Limit of Normal laboratory reference range) or missing at the baseline of the considered period and $>$ ULN under treatment.
 - Low emergent abnormal value under treatment according to the laboratory reference ranges is defined as value \geq LLN (Lower Limit of Normal laboratory reference range) or missing at baseline of the considered period and $<$ LLN under treatment.

- High emergent abnormal value under treatment according to the cut-offs for PCSA values is defined as value \leq ULS (Upper Limit used to define potentially clinically Significant abnormal values) or missing at baseline of the considered period and $>$ ULS under treatment.
- Low emergent abnormal value under treatment according to the cut-offs for PCSA values is defined as value \geq LLS (Lower Limit used to define potentially clinically Significant abnormal values) or missing at baseline of the considered period and $<$ LLS under treatment.

Analyses:

For each biochemical, haematological (blood and urine sample) parameter and for electrolytes monitoring (Potassium, Sodium), the following analysis will be performed for each period:

- Number and percentage of patients with at least one high/low emergent abnormal value under treatment, according to the laboratory reference ranges and to the cut-offs for PCSA values.
- Laboratory parameters classified (number and percentage of patients in each class) according to these reference ranges and cut-offs and using shift tables from baseline in the considered period to the worst (high and/or low) values under treatment.

Moreover, listings of patients with out-of-range or PCSA analysable values emergent under treatment in each period and of non-analysable values excluded from analyses will be provided.

Additionally, for potassium parameter, number and percentage of patients with hypokalaemia will be described by severity (mild: $3\text{mEq/L} \leq K^+ < 3.5 \text{ mEq/L}$ / moderate: $2.2\text{mEq/L} \leq K^+ < 3 \text{ mEq/L}$ / severe: $K^+ < 2.2\text{mEq/L}$) in each period.

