
All efficacy analyses will be performed in all randomized patients. The primary endpoint is defined as the change from baseline to 6 month in CARS2 total score. Primary analysis: bumetanide will be compared to placebo using a general linear model with baseline CARS2 and stratification factors as covariates. Missing data handling: CARS values post treatment discontinuation due to adverse event or lack of efficacy will be imputed using a reference based multiple imputation with a jump-to-reference approach. This approach assumes treatment benefit in patients who discontinue the Bumetanide arm disappears immediately upon discontinuation. Treatment effect estimation will take into account the situations when a patient can no longer tolerate or benefit from the treatment (occurrence of AE, lack of efficacy). CARS values post treatment discontinuation due to others reasons will be imputed using a classic multiple imputation approach assuming these patients could have theoretically continued to be treated without being put at undue risk. Sensitivity analysis: to assess the robustness of the results of the primary analysis, sensitivity analyses to the method of handling missing data will be performed including a mixed model for repeated measurement (MMRM).
 
Study participants (disposition, baseline characteristics and follow-up) and Safety analysis: Safety analysis: Safety analyses will be performed in the Safety Set defined as all included patients having taken at least one dose of study treatment. For every safety measurements, descriptive statistics will be provided by treatment groups.
 
Pharmacokinetic analysis: A population pharmacokinetic analysis will be performed to assess PK profiles of bumetanide in children. The population PK analysis will provide population PK parameters and their associated variability. In this analysis, the potential influence of covariates will be also investigated. Individual secondary PK parameters (such as AUC_{12,ss}, C_{min}) will be derived from the model for each patient. The population PK analysis will be detailed in a separate Data Analysis Plan. Exploratory assessment of the relationship between exposure and pharmacodynamics (efficacy and potentially safety) will be performed and if applicable, population PK/PD models will be developed and a Data Analysis Plan will be set up.
		
Contractual signatories		

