- All those measures contribute to the installation of a ritual much appreciated by patients with ASD.
- Sponsor highly recommends that the same person in charge of study evaluations follows a given child during the study in order to minimize any potential bias in study assessments and to reduce the burden linked to the potential stress suffered by the child.
- Paediatric liquid formulation has been specially developed for this paediatric clinical program. This formulation showed a good acceptability and palatability profile in the phase II.

For the benefit of the study, bumetanide could be the first pharmacological candidate allowing the treatment of ASD core symptoms in paediatric population, acting on a key component of the disease pathophysiology (alteration of GABAergic neurons and circuits, the conversion of GABA-mediated neuronal excitation into inhibition during maturation of specific neuronal populations being reported to be altered in neurodevelopmental diseases such as autism).

Acting centrally as a NKCC1 inhibitor, bumetanide provokes reduction of intracellular chloride, switching the aberrant excitatory action of GABA into an inhibitory action, and therefore may restore important developmental capacities.

Consequently, as there is no drug treatment for core symptoms of ASD, we set up a study with bumetanide in young developing patients with ASD in order to reduce the ASD core symptoms and functional impairment and to improve quality of life. Studies are needed in paediatric population, childhood being a time when brain plasticity is at the greatest and where behavioural and educative interventions could have the most benefit.

For the risk for the patient, the safety profile of bumetanide is similar to that reported for other loop diuretics. The target organ is the kidney and the safety profile is related to the potent diuretic activity of the compound. Based on the safety experience gained at this stage of drug development in ASD (5 clinical studies described above), the safety profile of bumetanide in ASD children and adolescents seems comparable to the one observed in adult patients treated for oedema. Despite the penetration of bumetanide into brain, no toxic effects on the Central Nervous System have been observed.

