10.2.2.6.2. Clinical laboratory evaluation

For clinical laboratory parameters, the following analyses will be performed by treatment period (double-blind treatment period and open-label active treatment period):

- Number and percentage of patients with at least one high/low emergent abnormal value under treatment, according to the laboratory reference ranges and to the cut-offs for PCSA values.
- Laboratory parameters classified (number and percentage of patients in each class) according to these reference ranges and cut-offs, and using shift tables from baseline to the worst (high and/or low) values under treatment.

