3.6.4. Vital signs, clinical examination and other observations related to safety

3.6.4.1. Vital signs and clinical examination

Definition:

- A value is considered as analysable if collected under appropriate circumstances.
- The analyses will be performed separately for periods #2, #4 and #6.
- A value is considered as occurring during the considered period if the associated visit date is between the start and last date of the considered period.
- Baseline for each period is defined in Section 3.1.2.

Analyses

The following vital signs and clinical examination will be analysed:

- Weight (kg).
- BMI (kg/m^2) (quantitative value and by class).
- HR (b.p.m).
- SBP (mmHg).
- DBP (mmHg).

Quantitative parameters will be described separately for each period, in terms of value at baseline, value at each planned post-baseline visit under treatment as well as in terms of change from baseline to each planned post baseline visit under treatment.

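### Laboratory data are summarised only against limits; value and change from baseline by visit are missing, so an average shift in potassium, creatinine or eGFR within the limits is never shown

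*SAP*

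**What the plan says.** SAP 3.6.3 covers each biochemical and haematological parameter and the sodium and potassium monitoring. It plans:

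- "Number and percentage of patients with at least one high/low emergent abnormal value under treatment, according to the laboratory reference ranges", and the same against the PCSA cut-offs;
- classification against those limits, "using shift tables from baseline in the considered period to the worst (high and/or low) values under treatment";
- "listings of patients with out-of-range or PCSA analysable values emergent under treatment in each period", plus a listing of non-analysable values;
- for potassium, "number and percentage of patients with hypokalaemia will be described by severity", in three classes that all lie below 3.5 mEq/L.

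Protocol 10.2.2.6.2 has the same counts and the same classification, "using shift tables from baseline to the worst (high and/or low) values under treatment". Neither section mentions a mean, a value by visit or a change from baseline.

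SAP 3.6.4.1 treats vital signs differently: "Quantitative parameters will be described separately for each period, in terms of value at baseline, value at each planned post-baseline visit under treatment", followed by change from baseline at those visits. SAP 3.6.4.2 does the same for ECG intervals. In the background section the protocol says of the drug: "The target organ is the kidney and the safety profile is related to the potent diuretic activity of the compound". It also calls hypokalaemia an identified risk.

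**The concern.** Counts and shift tables register a change only when a child crosses a limit. A child who moves from high-normal to low-normal stays in the same cell of the shift table and appears in no count and no listing. For example, an eGFR that falls from 125 to 95 crosses neither eGFR limit in the protocol (90 for entry in 5.4, 80 for stopping IMP in 5.6.1). It would show only if a laboratory or PCSA limit happened to catch it, and those limits are not given in the text.

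A loop diuretic is expected to move electrolytes and renal markers on average. The report could therefore show few abnormal values in both arms and give no estimate of the average effect on potassium, sodium or creatinine/eGFR. For vital signs and ECG intervals, the same report would give the by-visit change.

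**Working it through.** **The plan's own figure.** The laboratory sections state none. The only design calculation is for the primary endpoint (protocol 10.1, SAP 1.3): n per arm = 2 × [(1.960 + 1.282)/0.5]² = 84.1, so 85 per arm and 170 in total; 170/0.85 = 200. Both figures reproduce. They supply the arm sizes used below: 100 per arm included, 85 after 15% withdrawal.

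**Inputs from the documents.** Six planned double-blind potassium draws (48/72 h, Day 10, Day 17, W004, W012, W026) and two planned creatinine/eGFR draws (W012, W026), from protocol 8.2. Potassium limit 3.5 mEq/L (protocol 8.6, SAP 3.6.3). eGFR limits 90 and 80 (protocol 5.4, 5.6.1) stand in for the unstated laboratory limits.

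**Assumptions, not from the documents.** Normal values. Potassium: placebo mean 4.3, SD 0.35–0.45, uniform fall 0.2 mEq/L, within-child correlation 0.3–0.6. eGFR: mean 120, SD 15–20, fall 8, correlation 0.6, baseline above 90. Safety is descriptive, so two-sided 5% power serves only as a yardstick for information.

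**Formulas.** Means: SE = SD × √(2/n), power = Φ(Δ/SE − 1.96). Counts: power = Φ[(d − 1.96 × SE₀)/SE₁], where d is the difference in proportions and SE₀, SE₁ are the pooled and unpooled standard errors. The proportion with at least one low value was simulated (600,000 draws).

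**Potassium, one line in full** (SD 0.40, correlation 0.3, 100 per arm):
- Count: 11.2% against 27.7%, d = 0.166, SE₀ = 0.0560, SE₁ = 0.0547. Power = Φ[(0.166 − 0.110)/0.0547] = Φ(1.03) = 85%.
- Means at one visit: SE = 0.40 × √0.02 = 0.0566. Power = Φ(3.54 − 1.96) = 94%.

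| SD | At least one value < 3.5 in six draws, correlation 0.3 | Same, correlation 0.6 | Power, counts (100/arm) | Power, means (100/arm) | Power, means (85/arm) |
|---|---|---|---|---|---|
| 0.35 | 5.8% → 19.5% | 4.6% → 14.9% | 84%, 69% | 98% | 96% |
| 0.40 | 11.2% → 27.7% | 8.6% → 21.2% | 85%, 71% | 94% | 90% |
| 0.45 | 17.3% → 35.5% | 13.3% → 27.1% | 83%, 69% | 88% | 83% |

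If the placebo mean is 4.5 (SD 0.35–0.40), the counts drop to 33–56%.

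**eGFR, 100 per arm, at least one of two draws at or below the limit.** Baseline-adjusted SD = SD × √(1 − 0.6²) = 0.8 × SD.

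| SD | Limit | Placebo → active | Power, counts | Power, adjusted means at one visit |
|---|---|---|---|---|
| 15 | 90 | 3.2% → 10.5% | 54% | Φ(8/1.697 − 1.96) > 99% |
| 15 | 80 | 0.5% → 2.2% | 19% | > 99% |
| 20 | 90 | 8.2% → 17.6% | 51% | Φ(8/2.263 − 1.96) = 94% |
| 20 | 80 | 2.4% → 6.6% | 30% | 94% |

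With the eGFR mean varied over 115–125, the counts range over about 12–70%; the figures for means do not change. Simulation noise moves the count figures by about a point.

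**The case against.** Much of the case against stands and limits the point.

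- **A reader might infer that a fall in potassium would be invisible.** It would not. The plan counts children with any low value over the whole period, and six draws give many chances to cross 3.5. Using the prevalence at a single visit gives only 29–34% power for counts (SD 0.35–0.45), but that is not the planned statistic.
- **The means are not a clean measure either.** Low potassium leads to dietary advice and supplementation, and values below 3 mEq/L stop IMP (protocol 8.2, 5.6.1). Laboratory period #2 ends two days after last intake (SAP 3.6). The most affected children therefore leave or damp the later-visit means, while the worst-value tables keep them.
- **A reader might infer that repeat testing inflates the counts.** A retest follows an abnormal result, so that child is already counted. Retests can change only the worst value; the draws left to clinical opinion can affect both.
- **A reader might infer that laboratory data alone are reduced to categories.** In protocol 10.2.2.6.3.2 ECG is only a listing of abnormalities, and height is measured but not among the parameters in SAP 3.6.4.1.
- **A reader might see a contradiction with the synopsis**, which says "For every safety measurements, descriptive statistics will be provided by treatment groups". Protocol 10.2.2.1 and SAP 3.1.1 include numbers and percentages among descriptive statistics, so the counts can satisfy that sentence.
- **Other safeguards exist.** Potassium below 3.5 mEq/L is an event of special interest with immediate notification, and the DMC reviews all hypokalaemia. The table templates are a separate document and may hold more.

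None of this supplies the missing output. Monitoring protects individual children but does not estimate an average effect, and an unseen template does not replace a stated analysis.

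**Conclusion.** The point holds as a gap in the planned description. Every laboratory output in the SAP and protocol is tied to a limit, so movement within the limits is not displayed and larger movement shows only in part. For potassium the loss is moderate under the main assumptions: about 69–85% for the planned count against 88–98% for means (83–96% at 85 per arm). For parameters with two planned draws it is larger: about 19–54% for eGFR against 94% or more. These figures rest on assumed means, SDs, correlations and effects, and on 90 and 80 standing in for unstated eGFR limits. They ignore supplementation and stopping of IMP, which would narrow the advantage of means for potassium.

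The documents do not support saying that the trial would miss a diuretic effect on potassium, or that participants are left unmonitored.

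**What to change.** In SAP 3.6.3 add, for each quantitative laboratory parameter including locally measured sodium and potassium and creatinine/eGFR, the value and the change from the period baseline at each planned visit under treatment. Use the wording of 3.6.4: by treatment group in the SS for the double-blind period, in the SSO for the Placebo/S95008 arm, and in the SSC for the S95008/S95008 arm. Keep all existing counts, shift tables, listings and hypokalaemia classes.

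Between-arm differences with 95% CI for potassium and creatinine/eGFR in the double-blind period are optional and descriptive. They go further than what 3.6.4 gives for vital signs and ECG.

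The cost is programming and more tables, with no new data and no change to any clinical rule. Two notes should accompany the tables. First, double-blind baseline sodium and potassium are central while on-treatment values are local, so within-arm change mixes laboratories; randomisation stratified by country keeps the arms comparable. Second, supplementation and stopping of IMP damp later-visit potassium means, so these must be read beside the worst-value tables.
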